4.5.3. Cohort A and Cohort A1 Other Secondary Efficacy Variables

The secondary efficacy variables listed below include two types of variables: binary (B) and continuous (C) variables and marked for the corresponding cohort.

Other Secondary Efficacy Variables	Type	Cohort	
		A	A1
Proportion of subjects who have a symptomatic RT-qPCR confirmed SARS-CoV-2 infection (CDC definition) during the EAP	B	X	X
Number of weeks of symptomatic RT-qPCR-confirmed SARS-CoV-2 infection (CDC definition) during the EAP	C	X	X
Proportion of subjects who have a symptomatic RT-qPCR confirmed SARS-CoV-2 infection (strict-term) during the EAP	B	X	X
Number of weeks of symptomatic RT-qPCR-confirmed SARS-CoV-2 infection (strict-term) during the EAP	C	X	X
Proportion of subjects who have a RT-qPCR confirmed SARS-CoV-2 infection at each week in the EAP	B	X	X
Proportion of subjects who have a symptomatic RT-qPCR confirmed SARS-CoV-2 infection (broad term) at each week in the EAP	B	X	X
Time-weighted average of viral load (log10 copies/mL) from the first positive SARS-CoV-2 RT-qPCR in NP swab samples (that has an onset during the EAP) until the third weekly visit after the first positive test during the EAP	C	X	X
Note: Only for RT-qPCR positive subjects during the EAP in the Seronegative mFAS-A set			
Time-weighted average of viral load (log10 copies/mL) from the first positive SARS-CoV-2 RT-qPCR in NP swab samples (that has an onset during the EAP) until the second weekly visit after the first positive test during the EAP	C	X	X
Note: Only for RT-qPCR positive subjects during the EAP in the Seronegative mFAS-A set			
Maximum SARS-CoV-2 RT-qPCR viral load (log10 viral copies/mL) in NP swab samples among individuals with ≥ 1 RT-qPCR positive that has an onset during the EAP	C	X	X
SARS-CoV-2 RT-qPCR viral load (log10 viral copies/mL) in NP swab samples corresponding to the onset of first positive RT-qPCR during the EAP	C	X	X
Area under the curve (AUC) in viral load (log10 copies/mL) from the first positive SARS-CoV-2 RT-qPCR NP swab samples detected during the EAP until the first confirmed negative test (testing that occurs after the EAP will be included if necessary to achieve a negative test result).	C	X	X

Note: Only for RT-qPCR positive subjects during the EAP in the Seronegative mFAS-A set			
Number of medically attended visits in emergency rooms or urgent care centers related to a RT-qPCR confirmed SARS-CoV-2 infection that has an onset during the EAP	C	X	X
Proportion of subjects with at least one COVID-19 related hospitalization or emergency room visit associated with a positive RT-qPCR during the EAP, or all-cause death	B	X	X
Proportion of subjects requiring medically attended visits in emergency rooms or urgent care centers related to a RT-qPCR confirmed SARS-CoV-2 infection that has an onset during the EAP	B	X	X
Proportion of subjects hospitalized related to a RT-qPCR confirmed SARS-CoV-2 infection that has an onset during the EAP	B	X	X
Number of days of hospital and intensive care unit (ICU) stay in subjects hospitalized for a RT-qPCR confirmed SARS-CoV-2 infection that has an onset during the EAP	C	X	X
Number of days missed for daily responsibilities (where applicable), including work (employed adults) or school (students), daycare or family obligations/responsibilities (childcare or eldercare) due to a RT-qPCR confirmed SARS-CoV-2 infection that has an onset during the EAP	C	X	X
Proportion of subjects in placebo group with a RT-qPCR confirmed SARS-CoV-2 infection during the EAP with at least one household member participating either in R10933-10987-COV-2067 or in cohort B (comparison of those whose households members receive REGN10933+REGN10987 vs placebo in R10933-10987-COV-2067 or in Cohort B)	B	X	X
Proportion of subjects who have a symptomatic RT-qPCR confirmed SARS-CoV-2 infection (broad-term) during the EAP	B		X
Proportion of subjects with viral load >4 (log ₁₀ copies/mL) in NP swab samples during the EAP	B		X
Number of weeks of symptomatic RT-qPCR-confirmed SARS-CoV-2 infection (broad-term) during the EAP	C		X
Number of weeks of high-viral load >4 (log ₁₀ copies/mL) in NP swab samples during the EAP	C		X
Number of weeks of RT-qPCR confirmed SARS-CoV-2 infection (regardless of symptoms) during the EAP	C		X
Proportion of subjects who have a RT-qPCR confirmed SARS-CoV-2 infection (regardless of symptoms) during the EAP	B		X

Proportion of subjects in placebo group with a RT-qPCR confirmed SARS-CoV-2 infection during the EAP with an index case participating in R10933-10987-COV-2067 (comparison of those whose index cases receive REGN10933+REGN10987 vs placebo in R10933-10987-COV-2067)	C	X
--	---	---

Time-weighted average (TWA) of viral load (\log_{10} copies/mL) in NP swab samples from the day of the first positive SARS-CoV-2 RT-qPCR (central lab) to the third weekly visit after the first positive test visit: all observed viral load data from the first positive visit to the third weekly visit will be calculated using the trapezoidal rule as the area under the curve divided by this observational period as follows:

$$TWA = AUC/(t_k - t_1) = [\sum_{i=2}^{k=3} (t_i - t_{i-1}) * (V_i + V_{i-1})/2]/(t_k - t_1)$$

where V_i is the result of viral load (\log_{10} copies/mL) at time point t_i . V_1 is the result of the viral load (\log_{10} copies/mL) for the first positive SARS-CoV-2 RT-qPCR at timepoint t_1 . If the V_i is not available at the scheduled time point t_i or missing due to failed test or other reasons, only the time points with non-missing values will be included for TWA calculation. If there are duplicate samples at a time point, the highest viral result will be used for analysis.

Note: For TWA of viral from the first positive to the second weekly visit after the first positive test visit endpoint, all observed viral load data from the first positive visit to the second weekly visits will be calculated using the same formula described above.

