13. Samples for drug concentration and, immunogenicity, and laboratory testing will be collected based on the subject subset designation as indicated in [Table 4](#)
14. The serology test results will not be communicated to the sites. The sponsor's blinded study team will not have access to post-baseline results associated with subject identification until after the database is locked.
15. During each scheduled or unscheduled visit/contact, the investigator or designee will query subject about AEs in general (see Section [10.1.1](#)) and evaluate if the AEs are associated with SARS-CoV-2 infection, including fever (see Section [9.2.2.2](#)). The investigator should recommend that subjects (themselves or by their parent/guardian) measure their temperature daily during EAP, approximately at the same time, and also every time when the subject feels feverish, chills, or sick. Subjects with symptomatic SARS-CoV-2 infection should be queried on their symptoms weekly until symptoms resolve, even during follow-up period, then follow the regular schedule.
16. The information for the household assessment, including household members who receive an EUA approved monoclonal antibody treatment for COVID-19 or household members participating in the R10933-10987-COV-2067 study, should preferably be collected at the baseline visit. There will be a follow-up assessment at day 29.
17. All subjects will have a weekly NP swab sample collected during the EAP. Only subjects who are RT-qPCR positive will continue to have weekly NP swab samples collected during the follow-up period until 2 consecutive negative ( $\geq 24$  hr) RT-qPCR results or the end of study visit.
18. Only for RT-qPCR positive subjects (cohort A and cohort B): Complete assessments from the time the subject first becomes RT-qPCR positive or from the time they develop symptoms suspected to be COVID-19 (later confirmed by RT-qPCR positive results) until the subject has had 2 negative tests or COVID-19 related symptoms have resolved (whichever lasts longer), or until the end of study visit.

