The secondary and exploratory continuous efficacy endpoints such as TWA, AUC, and maximum viral load (\log_{10} copies/mL) will be analyzed using the ANOVA including treatment group, region, and age group as fixed effects in the model. The continuous endpoints regarding change from baseline in cohort B (e.g., TWA of change/percent change from baseline) will be analyzed using the ANCOVA model with treatment group, region, and age group as fixed effects, and the relevant baseline values as covariate as well as treatment-by-covariate interaction. The REGN10933+REGN10987 group will be compared to the placebo group and corresponding least square of mean difference, standard error (SE) and 95% confidence interval will be provided. For

other endpoints with non-normal/skewed distribution (e.g. number of days of symptoms (strict-term, and CDC definition, etc.)), Van Elteren test will be used.

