10.4. Example of SAS Procedures for Primary Analysis and Missing Data Imputations by FCS

Primary Analysis - GEE Model

Below is an example of SAS code using a generalized linear model to estimate the odds ratio between the treatment groups with the generalized estimation equation (GEE) approach after 100 imputations.

```
proc genmod data=DATA_IN;
class treatment(ref='0') Age_group region; /*eg.treatment= 0:placebo */
by _imputation_;
model response(event='1') =treatment region age_group/dist=bin link=logit;
repeat subject=household_id/type=cs;
lsmeans treatment/diff om cl ilink;
ods output diffss=logOR geeexchcorr=icc;
run;
```

Primary Analysis - Logistic Regression Model

Below is an example of SAS code using a logistic regression model instead of using GEE approach when the percentage of households with a single study subject is 70% or more to estimate the odds ratio between the treatment groups after 100 imputations.

```
proc genmod data=DATA_IN descending;
class treatment(ref='0') Age_group region;
by _imputation_;
model response(event='1') =treatment region age_group/dist=bin link=logit;
lsmeans treatment/diff om cl ilink;
ods output diffss=logOR ParameterEstimates=parameterestimates;
```

run;

Missing Data Imputations – FCS

Assume the missing RT-qPCR test results occurred across Visit 5 (Day 8) to Visit 8 (Day 29) (e.g. 1=positive vs 0=negative). An example of SAS code for FCS MI with the random seed=2069 is presented below.

```
proc mi data=DATAIN out=DATAOUT seed=2069 nimpute=100;
class treatment age_group region v5 v6 v7 v8;
var treatment age_group region v5 v6 v7 v8;
fcs logistic(v5/LIKELIHOOD=AUGMENT);
fcs logistic(v6/LIKELIHOOD=AUGMENT);
fcs logistic(v7/LIKELIHOOD=AUGMENT);
fcs logistic(v8/LIKELIHOOD=AUGMENT);
run;
```

After FCS MI to generate 100 complete datasets, each subject's overall RT-qPCR test status during the EAP can be determined by any of imputed value V5 to V8 is equal to 1. The same model using GEE approach or logistic regression for the primary analysis will be applied.

The results from the 100 analyses will be combined using Rubin's formulae through PROC MIANALYZE procedure shown below.

```
proc mianalyze data=logOR;
ods output parameterestimates=final_logor;
modeleffects estimate;
stderr stderr;
run;
```

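### The cohort A time-weighted average viral load is not taken over the same number of days in every infected subject, whichever way the SAP is read

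*SAP*

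**What the plan says.** - **Endpoints.** Two rows of the table in SAP 4.5.3 (and Protocol 4.1.3) define the average from the first positive swab: one "until the third weekly visit after the first positive test during the EAP", the other "until the second weekly visit after the first positive test during the EAP".
- **Calculation.** Below the table, the SAP states that "all observed viral load data from the first positive visit to the third weekly visit will be calculated using the trapezoidal rule" and divides by t_k − t_1. No EAP limit appears there. If a value is missing, "only the time points with non-missing values will be included for TWA calculation". The printed sum runs from i = 2 to k = 3.
- **AUC row of the same table.** Here "testing that occurs after the EAP will be included if necessary to achieve a negative test result". The two average rows carry no such sentence.
- **Swabs.** All subjects are swabbed on Days 8, 15, 22 and 29. After that, "Only subjects who are RT-qPCR positive will continue to have weekly NP swab samples collected during the follow-up period until 2 consecutive negative" results (Protocol 9.1.1, footnote 17; repeated in SAP 10.2.1). Footnote 9 adds that a subject negative at the end of the EAP is swabbed again only if symptomatic. Protocol 6.1.5 instead keeps anyone who turned positive during the EAP on weekly swabs until two negatives.
- **Conventions.** SAP 6.4, Table 4 has analysis windows for Week 5 onward. SAP 4.5 sets non-detectable RNA to 0 log10.
- **Lock and model.** The first-step lock waits only for EAP data (SAP 7). These endpoints "will be analyzed using the ANOVA including treatment group, region, and age group as fixed effects in the model", with nominal p-values at most (SAP 5.7.4).

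**The concern.** Viral load usually falls after detection. Averaging the same infection over fewer days therefore gives a higher value. When the divisor is the observed span, two subjects with identical infections can score differently because one was detected later, or because swabbing stopped when that subject cleared.

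That matters if the length of the window is related to treatment. Speed of clearance is something the drug is expected to change, and the timing of detection may be too. Part of any difference between arms would then reflect how long subjects were sampled. What is at stake is the estimated effect on viral load among cohort A subjects who became infected.

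**Working it through.** The plan gives no figure to reproduce. The inputs are the swab days (8, 15, 22, 29), the stopping rules and the SAP trapezoid.

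**1. Window length in days.** Let d be the day of first positive and m = 2 or 3 the target weekly visit. With EAP swabs only, window = min(7m, 29 − d). With later swabs allowed, take a fast clearer, negative at every swab after the first positive. Testing stops at the second negative, or at Day 29 under footnote 9.

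| First positive | EAP only, m = 3 | EAP only, m = 2 | Later swabs, fast clearer, m = 3 | Later swabs, fast clearer, m = 2 |
|---|---|---|---|---|
| Day 8 | 21 | 14 | 21 | 14 |
| Day 15 | 14 | 14 | 14 | 14 |
| Day 22 | 7 | 7 | 14 (7 under footnote 9) | 14 (7 under footnote 9) |
| Day 29 | 0 | 0 | 14 | 14 |

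At 0 days t_k = t_1 and the formula is 0/0. A slow clearer keeps 21 days when later swabs count. The fast clearer first positive at Day 8 also keeps 21, because everyone is swabbed weekly to Day 29.

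**2. Effect on the value.** The weekly log10 courses are assumed.

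- Course 5, 0, 0, 0: AUC = 7 × (5 + 0)/2 = 17.5. Average = 17.5/21 = 0.83; 17.5/14 = 1.25; 17.5/7 = 2.50.
- Course 7, 5, 3, 0: 7 × (6 + 4 + 1.5)/21 = 3.83; 7 × (6 + 4)/14 = 5.00; 7 × 6/7 = 6.00.

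**3. Direction.** Protocol 3.2.6 reports that active-arm infections in the administrative assessment lasted no more than 1 week, while about 40% of placebo infections lasted 3 to 4 weeks. When later swabs count, shortening therefore falls mainly on the active arm and raises its average.

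**4. Possible size when later swabs count.** Assume every active infection follows 5, 0, 0, 0 and every placebo infection 7, 5, 3, 0 with its full 21 days. With full windows in both arms the difference is 3.83 − 0.83 = 3.00. Two assumed mixes of first positives at Day 8/15/22/29 give these rises in the active mean:

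- 70/15/10/5%: 0.30 × 0.417 = 0.13. Under footnote 9: 0.20 × 0.417 + 0.10 × 1.667 = 0.25.
- 50/20/20/10%: 0.50 × 0.417 = 0.21. Under footnote 9: 0.30 × 0.417 + 0.20 × 1.667 = 0.46.

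So 0.13 to 0.46 of a 3.00 log10 difference would be lost under these assumptions.

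**5. EAP-only reading.** Give both arms the same assumed course 6, 4, 2, 0, with averages of 3, 4 and 5 over 21, 14 and 7 days. Day 29 positives drop out. The first mix gives (0.70 × 3 + 0.15 × 4 + 0.10 × 5)/0.95 = 3.37. The second gives (0.50 × 3 + 0.20 × 4 + 0.20 × 5)/0.90 = 3.67. Identical infections differ by 0.30 log10; equal mixes give no gap.

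**6. Printed index.** With t_1 as the first positive, k = 3 spans 2 × 7 = 14 days, which is the second weekly visit. The third needs k = 4, as cohort B uses for baseline to Day 22 (SAP 4.5.7).

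**The case against.** A reader might infer that the average is cut off at Day 29. The documents do not establish that. The EAP phrase can attach to the first positive test, the calculation text has no EAP limit, weekly swabs continue after Day 29, and Table 4 has windows for them. The AUC sentence and the timing of the lock point the other way, so the text is ambiguous.

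A reader might also infer that both windows run from 21 days to 0. The second-visit window starts at 14. If later swabs count it stays at 14 even for fast clearers, apart from the footnote 9 case.

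A third tempting inference is that the endpoint measures week of detection rather than the drug. It measures both. With assumed courses 6, 4, 2, 0 and 4, 1, 0, 0, the EAP-only third-visit difference is −2.0, −2.5 and −2.5 for first positives at Days 8, 15 and 22. On that reading bias requires the arms to differ in detection timing, and nothing in the plan shows that they do.

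Detection also appears to be early. Protocol 3.2.6 gives 10.3% of placebo and 5.4% of active subjects positive at Day 8. On 223 and 186 subjects that is 0.103 × 223 = 23 and 0.054 × 186 = 10, against about 30 events targeted. The same section counts 21 and 9 infected subjects, so the percentages probably use other denominators, but many infections were clearly seen at Day 8, where the window is full on either reading.

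Finally, these are other secondary endpoints outside the testing hierarchy. Maximum viral load and viral load at first positive do not use this window.

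All of this stands and limits the size. It does not remove the observed-span divisor, which shortens the third-visit window for fast clearers even on the more favourable reading.

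**Conclusion.** The point holds in limited form. The third-visit average has no common window on either reading. The second-visit average lacks one on the EAP-only reading and in the footnote 9 case. If later swabs count, the likely direction is to understate the drug's effect. That rests on 9 infected active-arm subjects in the administrative assessment behaving like those in the main analysis.

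The size is unknown. The figures above depend on assumed courses and detection mixes, and early detection makes a modest effect more likely. No confirmatory conclusion depends on it. The change is worth making because it is cheap and the definition needs correcting anyway.

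The absence of a detection-week term in the ANOVA might be read as a flaw to be cured by adding one. That does not follow. Week of first positive arises after randomisation and may itself respond to treatment, so adjusting for it can introduce bias.

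**What to change.** In SAP 4.5.3:

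1. State that the second and third weekly visits include post-EAP weekly swabs, assigned by the Table 4 windows.
2. Set scheduled visits after two consecutive negatives to 0 log10, the value already used for non-detectable RNA, so that the window is a fixed 14 or 21 days.
3. Give a rule for subjects with a single value and for those whose later swabs are unavailable at the first-step lock. A Day 29 positive needs swabs to Day 50 for the third visit. The rule must also cover a subject first positive at Day 22, negative at Day 29 and not swabbed again: one negative does not trigger item 2. Report the number of such subjects by arm.
4. Change the upper index to k = 4 for the third-visit average and give k = 3 for the second.
5. Report the observed-only average alongside, and show results by week of first positive descriptively only.

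Footnote 9 and Protocol 6.1.5 disagree on who is swabbed after Day 29 and must be reconciled.

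The cost is SAP wording and a small derivation change, with no added visits. The downside is that the zeros are assumed, not observed, which is why item 5 keeps the observed-only result.

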(students), or family obligations/responsibilities (childcare or eldercare) due to a RT-qPCR confirmed SARS-CoV-2 infection that has an onset at baseline or during the EAP			
Proportion of subjects with at least one COVID-19 related hospitalization or emergency room visit associated with a positive RT-qPCR at baseline or during the EAP, or all-cause death	B	X	X
Proportion of subjects who subsequently develop signs and symptoms (broad-term) within 14 days of a positive RT-qPCR at baseline or during the EAP	B		X
Number of weeks of symptomatic SARS-CoV-2 infection (broad-term) within 14 days of a positive RT-qPCR at baseline or during the EAP	C		X
Number of weeks of high viral load >4 (log10 copies/mL) in NP swab samples during the EAP	C		X

Time-weighted average (TWA) of change from baseline in viral load until the Day 22 visit: All observed viral load data from baseline to Day 22 visit will be calculated for each subject using the trapezoidal rule as the AUC for change from baseline at each time point divided by the time interval of this observational period as follows:

$$TWA = AUC/(t_k - t_1) = [\sum_{i=2}^{k=4} (t_i - t_{i-1}) * (D_i + D_{i-1})/2]/(t_k - t_1)$$

Where D_i is the change from baseline (t_1) in viral load (log10 copies/mL) obtained at time t_i and $D_1 = 0$. If the D_i is not available or missing due to failed test or other reasons, only the time points with non-missing values will be included for TWA calculation. If there are duplicate samples at a time point, the highest viral result (log10 copies/ml) will be used for analysis.

For TWA of percent change from baseline, variable P_i will be applied to the formula above instead of D_i , where $P_i = D_i/\text{baseline}$.

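### The cohort A time-weighted average formula is printed with k=3, one visit short of the third weekly visit that it is said to reach

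*SAP*

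**What the plan says.** SAP 4.5.3 lists two separate TWA endpoints for cohorts A and A1. One runs "until the third weekly visit after the first positive test during the EAP" and the other "until the second weekly visit after the first positive test during the EAP". Protocol 4.1.3 lists the same pair but gives no formula, so the SAP is the only place where the calculation is defined.

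Below the table, SAP 4.5.3 gives one formula, introduced for the longer endpoint: "all observed viral load data from the first positive visit to the third weekly visit will be calculated using the trapezoidal rule". The area is divided by the length of the period. The sum is printed from i=2 to k=3 and the divisor is t_k minus t_1. The starting index is fixed in words: V_1 is the viral load "for the first positive SARS-CoV-2 RT-qPCR at timepoint t_1". Only time points with non-missing values enter the calculation.

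A note then covers the shorter endpoint: "all observed viral load data from the first positive visit to the second weekly visits will be calculated using the same formula described above". It gives no other value of k.

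SAP 4.5.7 has a parallel formula for the TWA change from baseline in cohort B: "All observed viral load data from baseline to Day 22 visit will be calculated for each subject using the trapezoidal rule". There t_1 is baseline and the printed upper limit is k=4.

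**The concern.** The words and the printed limit in SAP 4.5.3 disagree. If the first positive test is point 1, the third weekly visit after it is point 4, so a sum that ends at k=3 leaves out the last weekly interval of the longer endpoint. Because the shorter endpoint is sent to the same formula, nothing in the printed mathematics separates the two.

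At stake is whether a named secondary endpoint covers the period that its title states. The values feed the ANOVA described in SAP 5.7.4. The exploratory TWA endpoints for baseline-seropositive subjects in SAP 4.5.4 use the same two end visits and have no formula of their own, so they would presumably inherit the same limit.

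**Working it through.** **Inputs**
- Start of the index: t_1 is the first positive test (SAP 4.5.3).
- Printed limits: i=2 to k=3, divisor t_k − t_1 (SAP 4.5.3).
- Sampling: weekly NP swabs in the EAP at Days 8, 15, 22 and 29 (SAP 10.2, Table 6 and footnote 17). Intervals of 7 days are nominal, because the visits have windows.
- Comparator: cohort B formula, k=4, baseline to Day 22 (SAP 4.5.7).

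**Index count.** With t_1 at the first positive test, the m-th weekly visit after it is t_(m+1). The second weekly visit is t_3 and the third is t_4.

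**Check against cohort B.** Baseline is Day 1 (t_1), followed by Day 8 (t_2), Day 15 (t_3) and Day 22 (t_4). Day 22 is the third weekly visit and needs k=4, which is what SAP 4.5.7 prints. The same convention applied to cohort A, with a first positive on Day 8, gives:

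| Upper limit | Last day | Weekly visit after first positive |
|---|---|---|
| k=3 (printed) | 22 | second |
| k=4 | 29 | third |

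**Size.** The documents give no subject-level viral loads, so the profiles below are assumptions. For log10 loads of 6, 5, 3 and 1 at 0, 7, 14 and 21 days after the first positive:
- k=3: [7 × (6+5)/2 + 7 × (5+3)/2] / 14 = (38.5 + 28) / 14 = 4.75
- k=4: [38.5 + 28 + 7 × (3+1)/2] / 21 = 80.5 / 21 = 3.83

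Other assumed profiles, calculated in the same way:

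| Loads | k=3 (printed) | k=4 |
|---|---|---|
| 7, 6, 4, 2 | 5.75 | 4.83 |
| 5, 3, 0, 0 | 2.75 | 1.83 |
| 4, 7, 5, 3 | 5.75 | 5.17 |
| 6, 6, 6, 6 | 6.00 | 6.00 |

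**The note on the shorter endpoint.** Taken literally it also uses k=3, so with complete weekly data both endpoints take the k=3 value. If it is read as one visit fewer (k=2), the endpoints differ but each ends a visit early. Neither reading of the printed limit produces both endpoints as named.

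**Missing visits.** For loads 7, 6, missing, 2 on Days 8, 15, 22 and 29, re-indexing the observed points gives t_3 = Day 29. Then k=3 yields [7 × 6.5 + 14 × 4] / 21 = 101.5 / 21 = 4.83, which does reach the third visit. The two endpoints therefore coincide exactly only when the weekly data are complete.

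**EAP limit.** If the phrase *during the EAP* restricts data to Day 29, a subject first positive at the Day 15 visit has only Days 22 and 29 left. There is no t_4, and k=3 already uses everything. Only subjects first positive by about Day 8 have a third weekly visit to lose.

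**The case against.** The strongest reply is that this is a slip in one index and the intended endpoints are not in doubt. The text names the end visit of each endpoint in the table, again in the definition, and again in the note, and it divides by the observed period. A programmer who follows the words would read the note as the same trapezoid over a shorter span and would get two different and correct values. That stands as a limit on the consequence, but it does not reconcile the printed limit with the sentence that introduces it.

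The endpoints also carry little inferential weight. They are other secondary variables, absent from the hierarchy in SAP 5.7.2, and SAP 5.7.4 says only that nominal p-values may be reported. Third-week data also enter the number-of-weeks endpoints and the AUC to first confirmed negative. The same formula applies in both arms, and nothing here shows a bias in the treatment comparison. All of this stands.

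A reader might infer that the two endpoints will always be the same number, or that the endpoint will in fact be computed over the wrong period. The documents do not support either: both depend on following the printed limit over the words, and identity also needs complete weekly data.

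A reader might also turn to Protocol 3.2.6, where about 40% of placebo infections lasted 3 to 4 weeks, as a measure of what is lost. That figure describes the administrative assessment, with 21 infected placebo subjects (about 8 people). SAP 3.1 excludes those subjects from the seronegative mFAS-A, so it does not measure the effect on this analysis.

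Finally, the point rests on a single digit in an equation, which should be confirmed on the typeset page of the SAP.

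**Conclusion.** The printed upper limit is wrong for the period it is said to cover. The definition of t_1 rules out an index that would make k=3 the third weekly visit, and the cohort B formula shows the SAP's own convention with k=4.

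For a subject with complete weekly data and a falling load, applying the printed limit overstates the third-visit TWA. The difference is 0.92 log10 copies/mL (4.75 − 3.83) for the assumed 6, 5, 3, 1 profile, between about 0.6 and 0.9 for the other non-flat profiles tried, and zero for a flat one. These sizes rest on assumed loads and nominal 7-day spacing.

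No primary or key secondary result, alpha allocation or power figure depends on the formula. It should be corrected because it is the only definition of a named endpoint, but it does not threaten the trial's main conclusions.

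**What to change.** In SAP 4.5.3, print k=4 for the TWA to the third weekly visit and state k=3 for the TWA to the second.

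Add one sentence saying that t_k is the last non-missing time point up to the named visit. A fixed k alone does not fit the rule that only observed points are used. For example, with a first positive on Day 8, no value on Day 22, and weekly swabs continuing after the EAP, the fourth observed point would be Day 36, beyond the third weekly visit. The same sentence should say whether *during the EAP* limits the data to Day 29.

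Apply the definition by cross-reference to the seropositive TWA endpoints in SAP 4.5.4.

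The cost is one digit and a short note. No data collection, sample size or testing order changes. It belongs in the SAP before the first-step database lock and unblinding, which is the deadline that SAP Section 1 sets for the final plan.
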